## 5 Changes in the Conduct of Planned Analyses

Changes after finalization of this SAP will either be described in a protocol amendment or in an update to the SAP. They will be clearly indicated in the CSR.

Changes in the analysis following Amendment 2 are as follows:

Efficacy analysis: the planned treatment for the efficacy analysis is the randomized treatment. Following Amendment 2, for subjects randomized to [REDACTED] mg CSL312 q4wk in Treatment Period 2 their planned treatment will be reduced to [REDACTED] mg CSL312 q4wk. The subjects will be reported under this treatment after the planned dose reduction. For subjects who receive continuously the same dose of CSL312 during both treatment periods, data will be included in the analysis until the planned dose reduction following Amendment 2.

Safety analysis: the actual treatment will be used for the Safety analysis. Subjects with planned or unplanned dose reduction or allowed dose increase will be reported under the treatment they actually received. For subjects who receive continuously the same dose of CSL312 during both treatment periods, data will be included in the analysis until any dose change.

The second and third interim analysis will be combined into one.

## 6 Study Analysis Populations

### 6.1 Screening Population

The Screening population will consist of all subjects who provide written informed consent and who undergo any study screening procedure.

Technical Note: Subjects with informed consent date available and any assessments labelled as Screening Visit available will be included.

## 6.2 Intent-to-Treat Population

The Intent-to-Treat (ITT) population will consist of all subjects who provide informed consent, undergo any study screening procedure, and who are assigned to treatment in Treatment Period 1 or to treatment in Treatment Period 2, regardless of whether they receive the investigational product. The ITT population will be analyzed using the treatment to which the subject was assigned in Treatment Period 1, in Treatment Period 2 at Week 13, or [REDACTED] mg after dose reduction from [REDACTED] mg following Amendment 2 in Treatment Period 2 (only applicable for C1-INH HAE subjects), regardless of the actual treatment received.

Technical Note: Subjects who belong to the Screening population and have randomization date available for Treatment Period 1 or Treatment Period 2 will be included for the corresponding Treatment Periods. Thus, the ITT will be assigned within treatment period.

## 6.3 Safety Population

The Safety population will consist of all subjects who provide informed consent, are assigned to treatment in Treatment Period 1 or to treatment in Treatment Period 2 and receive at least 1 dose or partial dose of the investigational product and will be based on the actual treatment received.

Technical Note: Subjects who belong to the ITT population and have at least one non-missing volume of study medication entered in the eCRF will be included.

## 6.4 Per-Protocol Population

The per-protocol (PP) population will consist of all subjects in the ITT population, excluding subjects who have a significant protocol violation. Protocol violations which will lead to exclusion from the PP population will be reviewed and agreed prior to conducting each of the interim analyses and before database lock.

Technical Note: Subjects who belong to the ITT population and who do not have significant protocol violations which lead to exclusion from PP as decided during the Data Review Meeting will be included.

## 6.5 Pharmacokinetic Population

The PK population will consist of all subjects in the Safety population for whom at least 1 measurable concentration of CSL312 is reported.

**6.6** CCI [REDACTED]

CCI [REDACTED]

**7 General Considerations**

Analysis datasets will be created according to Clinical Data Interchange Standards Consortium (CDISC) standards, and data will be displayed according to reporting standards in this SAP and TFL formats.

SAS version 9.3 or higher will be used to perform all data analyses and to generate TFLs.

All ICH required data in the database will be presented in data listings.

Depending on the analysis populations defined, all data from a subject or a subset of data may be excluded from certain analyses (e.g., analyses based on the PP population) as defined in Section 6.

Continuous variables will be described by the number of observations, mean values with their 95% CIs, standard deviation (SD), 25th percentile, median (50th percentile), 75% percentile, and range (minimum to maximum). The geometric coefficient of variation will be expressed as a percentage for PK and CCI data and will be calculated as  $100 \cdot \sqrt{\exp(\text{SD}_{\log}^2) - 1}$ . The geometric mean and its 90% CI will be calculated for PK and CCI data. The geometric mean and its 90% CI will be calculated by log-transforming the data, calculating the mean and the lower and upper limits of the 90% CI of the log-transformed data, and subsequently back transforming the mean and the lower and upper limits. Categorical variables will be summarized using frequency counts and percentages. Analyses that use other descriptive statistics will have the specific descriptive statistics required identified with the analysis in the applicable SAP section.

Summary statistics of location parameters (mean, median, quartiles) will be reported to one more decimal place than the collected data. Summary statistics of variability (SD) will be reported to one more decimal place than the commensurate location parameter. For example, the mean and median for age will be reported to one decimal place because it is collected in full years. The SD of age will then be reported to 2 decimal places. Descriptive percentages and proportions will be displayed to one decimal place. Percentages and proportions to be tested will be calculated to 4 decimal places. Durations will be display to 1 decimal place.

The data from Treatment Period 1 and Treatment Period 2 will be analyzed separately. For subjects who received continuously the same dose of CSL312 during both treatment periods, the two treatment periods will also be analyzed together. For C1-INH subjects having a dose change in Treatment Period 2, only data until the date and time of the dose change will be included in these summaries over both treatment periods for the safety analyses. For efficacy analyses, data until the date and time of the planned dose reduction will be included in these summaries over both treatment periods.

In Treatment Period 1, subjects with C1-INH HAE who are treated with placebo, [REDACTED] mg, [REDACTED] mg, or [REDACTED] mg CSL312 q4wk will be analyzed separately from subjects with C1-INH HAE who are treated with [REDACTED] mg CSL312 q2wk. In both treatment periods, subjects with FXII/PLG HAE will be analyzed separately from subjects with C1-INH HAE.

Summaries will be reported by treatment period and treatment in the following order:

- Treatment Period 1 FXII/PLG HAE: [REDACTED] mg CSL312 q4wk;
- Treatment Period 2 FXII/PLG HAE: [REDACTED] mg CSL312 q4wk;
- Treatment Period 1 & 2 FXII/PLG HAE: [REDACTED] mg CSL312 q4wk;
- Treatment Period 1 C1-INH HAE: placebo, [REDACTED] mg, [REDACTED] mg, and [REDACTED] mg CSL312 q4wk, Total Blinded Part and Total CSL312 (no totals will be populated for efficacy; for PK, [REDACTED] only Total CSL312);
- Treatment Period 1 C1-INH HAE: [REDACTED] mg CSL312 q2wk;
- Treatment Period 2 C1-INH HAE: [REDACTED] mg (initial and after down-titration), [REDACTED] mg in the Safety analysis], [REDACTED] mg CSL312 q4wk, and Total (no total will be populated for efficacy);
- Treatment Period 1 & 2 C1-INH HAE: [REDACTED] mg, [REDACTED] mg CSL312 q4wk, and Total (no total will be populated for efficacy) – only data included until dose change (Safety analysis) or planned dose reduction (Efficacy analysis).

The by-subject listings will include treatment period, treatment, subject number, and basic demographics (sex, age, body mass index [BMI]), and the information specific to that listing. The laboratory normal reference ranges will be provided and clinical laboratory test results outside the normal reference range will be flagged in the laboratory data listings.

The by-subject listings will be sorted by the treatment which the subjects will be assigned to in Treatment Period 1 in combination with the treatment they will be assigned to in Treatment Period 2, subject number, and then by visit / date and time. The planned dose reduction

following Amendment 2 or dose increase according to the protocol and any unplanned dose reductions will happen on an individual base and will be reported in the listings. The dose changes will not affect the treatment sequences. The treatment sequences for sorting will be as follows:

Treatment Period 1	Treatment Period 2
Subjects With C1-INH HAE	
Placebo q4wk	none
Placebo q4wk	cc1 mg CSL312 q4wk
Placebo q4wk	cc1 mg CSL312 q4wk
cc1 mg CSL312 q4wk	none
cc1 mg CSL312 q4wk	cc1 mg CSL312 q4wk
cc1 mg CSL312 q4wk	cc1 mg CSL312 q4wk
cc1 mg CSL312 q4wk	none
cc1 mg CSL312 q4wk	cc1 mg CSL312 q4wk
cc1 mg CSL312 q4wk	none
cc1 mg CSL312 q4wk	cc1 mg CSL312 q4wk
cc1 mg CSL312 q2wk	none
cc1 mg CSL312 q2wk	cc1 mg CSL312 q4wk
cc1 mg CSL312 q2wk	cc1 mg CSL312 q4wk
Subjects With FXII/PLG HAE	
cc1 mg CSL312 q4wk	none
cc1 mg CSL312 q4wk	cc1 mg CSL312 q4wk

Formatting for dates and times will be:

- Dates only – ddmmmyyyy;
- Times only – hh:mm or hh:mm:ss (as appropriate);
- Dates and times – ddmmmyyyy hh:mm or ddmmmyyyy hh:mm:ss (as appropriate).

Generally, only pre-specified planned times will be used in the summaries, statistical analyses, and calculations of any derived parameters; unscheduled assessments will be included in the listings.

Actual, rather than planned, sampling times will be used in the derivation of PK parameters and in the individual concentration-time plots and listing of PK concentration data. Planned times will be used in the descriptive summaries and in mean and median plots.

Concentration-time data will be listed according to actual sampling times relative to dosing time.

Assessment windows will not be defined for classifying measurements obtained outside scheduled assessment times.

### 7.1 Multicenter Studies

Data from all participating sites will be pooled prior to analysis. The site identifier will be populated in the listings along with the subject number.

### 7.2 Treatment Descriptors

C1-INH HAE: Treatment Period 1 Blinded			
Placebo q4wk	●●● mg CSL312 q4wk	●●● mg CSL312 q4wk	●●● mg CSL312 q4wk

C1-INH HAE Treatment Period 1 Open-label
●●● mg CSL312 q2wk

C1-INH HAE: Treatment Period 2 Open-label		
CCI mg CSL312 q4wk	CCI mg CSL312 q4wk	CCI mg CSL312 q4wk

**CCI** mg CSL312 will be included only for the Safety analysis; **CCI** mg will include planned (for Efficacy and Safety analysis) and unplanned dose reduction for Safety analysis.

FXII/PLG HAE: Treatment Period 2 Open-label
CCI mg CSL312 q4wk

### 7.3 Multiple Comparisons and Multiplicity

See Section 10.1 for details.

## 8 Data Handling Conventions

### 8.1 Missing Data

#### 8.1.1 Imputation of Non-Date Missing Data

Missing data occurs when any requested data is not provided, leading to blank fields on the collection instrument. These data will be indicated using a “blank” in subject listing displays. Answers such as “Not applicable” and “Not evaluable” are not considered to be missing data and should be displayed as such.

Only missing values for the primary efficacy endpoint (i.e., time-normalized number of HAE attacks) during Treatment Period 1 will have an impact on the analyses of the pairwise comparison between **CCI** mg CSL312 q4wk versus placebo q4wk and **CCI** mg CSL312 q4wk versus placebo q4wk in Treatment Period 1. The time-normalized number of HAE attacks will only be missing for subjects receiving investigational product q4wk and q2wk who drop out before Day 6 and Day 15, respectively, of Treatment Period 1.

Imputation methods based on Markov-Chain Monte Carlo (MCMC) techniques assume a certain distribution of the data and sample from this distribution values which are imputed to replace the missing values. With only 8 subjects per treatment, MCMC methods are not expected to yield reliable estimates. Instead a systematic approach (Enhanced Tipping Point

analysis [[Liublinska and Rubin, 2014](#)]) will be applied to investigate the robustness of the study's conclusion to the assumed missingness pattern. For details see Section [10.1.1](#).

Subjects with the assessment of treatment relationship for AEs and SAEs missing will have the worst case assumed to impute the relationship: if relationship to study treatment is missing and the event started on or after the first administration of study treatment it will be assumed to be "Yes". There will be no other imputation for missing data.

### 8.1.2 Imputation of Partial Dates

If the start or end date of an event is missing, then the duration of the event will naturally also be missing.

There will be no imputation of partially or completely missing dates. See Section [11.2](#) for the handling of partially or completely missing AE start dates. See Section [0](#) for the handling of partially or completely missing start and end dates of concomitant medication.

## 8.2 Derived Variables

The following sections provide a general description of the derived variables for data analyses. Analysis dataset specifications in a separate document will provide full details on data derivations and transformations.

### 8.2.1 Reference Dates

Reference dates are used to assign study periods relative to treatment.

Because age is an eligibility criterion, the reference date for age will be the date of Screening.

The safety reference date will be the treatment start date and will be used to calculate study day for safety measurements.

The efficacy reference date will be the start date of the efficacy evaluation period.

### 8.2.2 Study Day for Safety and Efficacy Measures

If the date of interest occurs on or after the safety or efficacy reference date, then the study day will be calculated as (date of interest – safety or efficacy reference date) + 1. If the date of interest occurs before the safety or efficacy reference date, then the study day will be calculated as (date of interest – safety or efficacy reference date). There will be no Day 0.

### 8.2.3 Durations

Durations (e.g., the duration of an AE) will be calculated in days:

- End date and time (if available) – start date and time (if available) + 1.

CCI

To transform durations or CCI which are calculated in days into months, divide the number of days by 30.4375; to transform to weeks divide the number of days by 7; to transform to years divide the number of days by 365.25. These algorithms return decimal numbers and ignore the actual numbers of days in the months or years between start date and stop date. The "year" used in these algorithms is 365.25 days long, and the "month" is one twelfth of that year.

Age will be taken from the data base.

### 8.2.4 Baseline Definition

Baseline is defined as the most recent, non-missing value prior to or on the first study treatment dose date.

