Viral serology ^a	
 A blood sample will be retained for potential assessment of viral serology
Immunogenicity ^a	
 Binding antibodies (inhibitory and non-inhibitory) specific to FXIIa antagonist monoclonal antibody.

Abbreviations: CCI [REDACTED]; C1-INH HAE = Hereditary angioedema with C1-esterase inhibitor deficiency; FXIIa = activated factor XII; FXII/PLG HAE = Hereditary angioedema with normal C1-esterase inhibitor and factor XII or plasminogen gene mutation; HAE = hereditary angioedema.

Footnotes:

^a Analysis will be conducted at a central laboratory. Additional details are provided in the Laboratory Manual.

^b CCI [REDACTED] will be measured as a part of the coagulation panel for assessment of safety, but will also be analyzed as CCI [REDACTED] (Table 7).

Laboratory Parameters

Details related to the collection, preparation, and transfer of blood and urine samples for laboratory assessments will be provided in the Laboratory Manual.

Refer to [Section 9.6.4](#) for assessment of abnormal laboratory values. Tests resulting in abnormal laboratory values during the study period that have been classified by the investigator as clinically significant should be repeated as soon as possible after receiving the laboratory report to rule out laboratory error.

Vital Signs

Blood pressure and heart rate will be measured with the subject in a supine or seated position after resting for at least 5 minutes. Body temperature will be measured either sublingually or tympanically, and the method of measurement should be consistent throughout the study for a given subject.

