8.5.2.1 Week 1 (Day 1) Visit

The following procedures will be conducted at the Week 1 (Day 1) Visit:

- Confirm eligibility for entry into Treatment Period 1.
- Assignment to treatment with the investigational product.
- Physical examination.
- Vital signs, including weight.
- CCI
- CCI
- Collection of urine for urinalysis.
- Collection of urine or blood for pregnancy test (for women of childbearing potential). A serum pregnancy test will be performed by the site if urine result is inconclusive.
- Collection of blood to assess:
 - Hematology.
 - Biochemistry.
 - Coagulation.
 - Viral serology (retention sample).
 - PK / CCI (pre-dose and 0.5, 4.0, and 8.0 hours post-dose).
 - Immunogenicity.
- Review eDiary instructions with subject.
- Review eDiary data, including investigator assessment of HAE symptoms and documentation of HAE attacks.

- Confirm access to on-demand HAE medication.
- Intravenous administration of investigational product by investigator or delegate.
- Accountability of investigational product.
- Concomitant medications and therapies.
- Adverse events.

Note 1: The physical examinations, vital signs, weight measurement, and collection of blood and urine for laboratory assessments must occur before administration of the investigational product.

Note 2: The PK / **COI** blood draws at 4.0 hours (\pm 60 minutes) post-dose and 8.0 hours (\pm 120 minutes) post-dose at the Week 1 (Day 1) Visit should occur \geq 120 minutes apart.

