### 8.2.6 Multiple Assessments

All data will be reported according to the nominal visit date at which it was assessed (that is, no visit windows will be applied during dataset creation and the visit will not be re-allocated if the actual visit date deviates from the planned date according to the visit schedule in the

protocol). If multiple assessments for the same visit occur, it will be distinguished why this is the case. If a laboratory sample was repeated due to technical problems the results from the valid sample(s) for this visit will be used in the analysis. If a laboratory sample was repeated as safety follow-up to monitor abnormal values of the initial sample, the initial sample (revealing the abnormal values) of this visit will be used in the analysis.

Data from all assessments (scheduled and unscheduled), including multiple assessments, will be included in listings.

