## 11.10 Clinical Laboratory Evaluations

Laboratory tests will be summarized descriptively by scheduled visit as specified in Section 7. For laboratory test with continuous values, descriptive statistics for the measured values and for change from baseline will be presented. Definition of the baseline assessment can be found in Section 8.2.4. Laboratory tests with categorical values will be summarized by number and percentage of subjects in the respective categories (based on subjects of the Safety population with non-missing values at this time point). Summary tables will be provided for hematology, biochemistry, coagulation, and immunogenicity (inhibitory and non-inhibitory antibodies). All laboratory tests (scheduled and unscheduled) will be listed. The listings will include the variables as specified in Section 7 and in addition the laboratory

test name and unit along with normal range, the sampling date and time, the test result, an assessment whether the result is high (above normal range) or low (below normal range). Any comments to the laboratory test will be provided in a separate listing.

A by-subject listing for laboratory abnormalities will be provided in the same format as the laboratory listings described above but only containing information about abnormal laboratory results.

The number and percentage of subjects who experience antibodies (inhibitory and non-inhibitory) specific to FXIIa will be summarized as a secondary (for subjects with C1-INH HAE) and CCI in this study. Percentages will be based on subjects of the Safety population with non-missing values at each time point.

The number and percentage of subjects with abnormal laboratory values reported as AEs will be summarized by laboratory test and visit and for all laboratory tests combined as a further secondary (for subjects with C1-INH HAE) and CCI. The laboratory findings reported as AEs will be identified through the eCRF. Percentages will be based on subjects of the Safety population with non-missing values at each time point.

The laboratory tests will be presented in the following grouping and sequence as specified in Table 6 of the protocol. The test names used in the TFLs may differ depending on the terminology used by the central laboratory. The test names and units as provided in the laboratory data transfer will be used.

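### SAP 8.2.4 sets baseline by dose date, not dose time, so for analytes sampled serially on Day 1 the rule as written selects the 8-hour post-dose value

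*SAP*

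**What the plan says.** The general rule, in SAP 8.2.4, is: "Baseline is defined as the most recent, non-missing value prior to or on the first study treatment dose date". SAP 8.2.5 builds change and percentage change from baseline on it. For laboratory change from baseline, SAP 11.10 refers back to it: "Definition of the baseline assessment can be found in Section 8.2.4".

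Protocol 8.5.2.1 covers the Week 1 (Day 1) Visit for subjects who start with an IV loading dose, namely the four blinded C1-INH HAE arms and the FXII/PLG HAE arm. The first dose is given at that visit ("Intravenous administration of investigational product by investigator or delegate"). The PK and redacted-analyte draws are scheduled "pre-dose and 0.5, 4.0, and 8.0 hours post-dose". Hematology, biochemistry, coagulation and immunogenicity are listed once each, with no post-dose times. A note to the visit requires that "collection of blood and urine for laboratory assessments must occur before administration of the investigational product".

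Two other SAP rules bear on which record is used. Section 7 says: "Generally, only pre-specified planned times will be used in the summaries, statistical analyses, and calculations of any derived parameters". Section 8.2.6 says: "If multiple assessments for the same visit occur, it will be distinguished why this is the case". It then settles two cases: technical repeats (use the valid sample) and safety follow-up repeats (use the initial sample).

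**The concern.** A baseline should be a value not yet influenced by treatment. The SAP's rule admits any value on the calendar date of first dose and prefers the latest. That is harmless when the only Day 1 value is taken before dosing. It is not harmless when the same analyte is scheduled again later that day.

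What is at stake is the change and percentage change for the serially sampled analytes. Protocol 3.3.2 expects the IV loading dose to raise plasma concentration at once above the later steady-state trough, so an 8-hour sample in an active arm is taken under substantial exposure. Measured from there, a drug effect would shrink, vanish or change sign, while placebo would keep an untreated reference. The distortion would therefore fall on the between-arm contrast and differ by dose.

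**Working it through.** No sample size, power, alpha or event figure depends on this rule, so there is no stated figure to reproduce. The check applies the rule to the Day 1 schedule.

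**Step 1: which record is selected.** The candidate records for a serially sampled analyte are any Screening value, pre-dose, 0.5 h, 4 h and 8 h.

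| Rule | Serial Day 1 sampling | Single pre-dose Day 1 draw |
|---|---|---|
| SAP 8.2.4: latest record with date ≤ date of first dose | 8 h post-dose | pre-dose |
| Latest record with date and time before first dose | pre-dose | pre-dose |

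This assumes that the 8 h draw falls on the dosing date. If the 8 h value is missing, the rule moves to the 4 h value, which is also post-dose.

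**Step 2: whether another visible rule prevents it.**
- SAP 7 keeps planned times, and 8 h is a planned time.
- SAP 8.2.6 decides only between an initial sample and a repeat, so planned serial samples fall outside it.
- SAP 12.2 treats pre-dose samples specially for concentration summaries but defines no baseline.
- The note in Protocol 8.5.2.1 on drawing blood before dosing cannot govern samples that the same visit schedules after dosing.

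**Step 3: who is exposed.** Up to 24 blinded active subjects (3 arms × 8) and 10 FXII/PLG subjects would get an on-drug baseline. For the 8 placebo subjects the selected record is also the 8 h one, but it carries no drug effect. Protocol 8.5.3.1 lists no post-dose Day 1 times for the q2wk arm, which is not exposed.

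**Step 4: size, as an illustration.** Set the pre-dose value to 1, let I be the inhibition at a later visit and I8 the inhibition at 8 h. By the SAP 8.2.5 formula:
- with a pre-dose baseline, percentage change = −100 × I;
- with the 8 h baseline, percentage change = 100 × [(1 − I)/(1 − I8) − 1].

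The documents give no value for I8, so it is an assumption and is varied. The values of I are the target levels in Protocol 3.3.2 (30%, 50%, 90%), used only as a convenient grid.

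| True change | I8 = 0% | I8 = 30% | I8 = 50% | I8 = 90% |
|---|---|---|---|---|
| −30% | −30% | 0% | +40% | +600% |
| −50% | −50% | −28.6% | 0% | +400% |
| −90% | −90% | −85.7% | −80% | 0% |

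Worked entry: true change −50%, I8 = 30% gives 100 × (0.5/0.7 − 1) = −28.6%. Whenever I8 equals I, the derived change is 0%.

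**The case against.** The strongest reply is that no visible analysis goes wrong. The visible change-from-baseline summaries are laboratory tests (SAP 11.10) and vital signs (SAP 11.11.1). On Day 1 these are done before dosing, so both rules pick the same record. The visible PK parameters are not changes from baseline, and the responder analysis compares with the Run-in Period. All of this stands.

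A reader might infer that repeat samples contaminate the safety baselines generally. The documents do not support that. SAP 8.2.6 keeps the initial sample for safety follow-up repeats, and SAP 7 sends unscheduled assessments to the listings. Only a technical repeat drawn after dosing on Day 1 remains exposed.

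A reader might also infer that a safety coagulation test is itself sampled serially, because a Table 6 footnote in Protocol 8.1.1 says that one redacted parameter "will be measured as a part of the coagulation panel for assessment of safety, but will also be analyzed as" something further, also redacted. The footnote says only that a coagulation-panel measurement is used in a second analysis. It does not say that the parameter is measured at 0.5, 4 and 8 hours, and the Day 1 coagulation draw is listed separately from the serial line.

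Finally, SAP 8.2 calls its definitions general and leaves full derivations to separate dataset specifications, and a careful programmer would probably choose the pre-dose sample. That makes an actual error less likely but does not cure the text. Section 8.2.4 does not leave the choice open. It states a rule, and following it gives the wrong record.

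**Conclusion.** The defect is in the general baseline definition. For analytes sampled serially on Day 1 in subjects given an IV loading dose, SAP 8.2.4 read literally selects the 8-hour post-dose value, and no visible passage overrides it.

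The practical effect is confined to the redacted analytes drawn on the serial schedule. It runs from none, if the redacted sections define their own baseline or use no change from baseline, to a wrong baseline for essentially every such subject with an 8-hour sample. It would go too far to say that those analyses are wrong, because they cannot be seen and redacted text is not missing from the plan. One indication that the rule matters is that the percentage-change formula in SAP 8.2.5 is used in no visible analysis, so it probably serves a redacted one. That is an inference.

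The figures in the illustration rest on assumed 8-hour inhibition. The primary endpoint, the alpha split, the sample size and the responder analysis are untouched. Priority is low.

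**What to change.** Replace the sentence in SAP 8.2.4 with:

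> Baseline is the last non-missing value with date and time before the date and time of the first administration of study treatment; if the time is missing, the nominal pre-dose sample is used.

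This matches the SAP's practice elsewhere, since treatment-emergent events (11.3) and evaluation periods (8.2.8) are already defined by date and time. It also closes the remaining gap for a technical repeat drawn after dosing on Day 1. Analytes with a single pre-dose draw keep the same baseline.

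If the redacted sections already define a pre-dose baseline, a cross-reference from 8.2.4 would remove the conflict between the two texts.

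The cost is one sentence. The SAP's listings already call for the date and time of the first IV dose (9.1) and of laboratory sampling (11.10), so no new data and no change in trial conduct are needed.
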